9.		MONITORING, AUDIT, AND INSPECTION	59
1().	ETHICAL AND REGULATORY CONSIDERATIONS	59
	10.1.	Research Ethics Committee (REC) review and reports	59
	10.2.	Peer review	60
	10.3.	Public and patient involvement	60
	10.4.	Protocol compliance	61
	10.5.	Notification of Serious Breaches to GCP and/or the protocol	61
	10.6.	Data protection and patient confidentiality	62
	10.7.	Financial other competing interests for the CI, PI's, and committee members	62
	10.8.	Indemnity	62
	10.9.	Amendments	63
11	1.	DISSEMINATION POLICY	63
	11.1.	Authorship eligibility guidelines	64
12	2.	REFERENCES	64
13	3.	APPENDICIES	68
	13.1.	Appendix 1: Risk	68
	13.2.	Appendix 2: Amendment History	70

ii. LIST OF ABBREVIATIONS

30 SCSST 30 Second Chair Sit-to-Stand Test

AE Adverse Event
AR Adverse Reaction
CI Chief Investigator
CRF Case Report Form

EQ-5D-5L Euroqual 5 Dimensions
GCP Good Clinical Practice

ISF Investigator Site File (This forms part of the TMF)

ISRCTN International Standard Randomised Controlled Trials Number

MRS Modified Rankin Scale

NIHSS National Institute of Health Stroke Scale

NHS R&D National Health Service Research & Development

NPRS Numerical Pain Rating Scale

PI Principal Investigator

PIS Participant Information Sheet

PAG Public Advisory Group

QA Quality Assurance

QC Quality Control

RCT Randomised Control Trial
REC Research Ethics Committee

SAE Serious Adverse Event
SAR Serious Adverse Reaction

SNMES Surface Neuromuscular Electrical Stimulation

SOP Standard Operating Procedure

SUSAR Suspected Unexpected Serious Adverse Reaction

TMF Trial Master File

TMG Trial Management Group
TSC Trial Steering Committee

TUG Timed up and Go

UHD University Hospitals Dorset NHS Foundation Trust

VAS Visual Analogue Scale (pain)

IRAS ID: 332116 Page **7** of **70**

iii. TRIAL SUMMARY

Using surface neuromuscular electrical stimulation for lower limb weakness early after stroke: A randomised controlled feasibility study		
STIM-Stroke		
Mixed methods randomised controlled feasibility study with nested qualitative component (interviews and focus group)		
Patients within 2-weeks of stroke	(n=60)	
Caregiver/significant other to pers the experimental group (n=10)	on with stroke who was randomised to	
Clinicians supporting the trial (n=1	0)	

Assess the feasibility and acceptability of lower limb surface neuromuscular electrical stimulation (SNMES) started within 2 weeks after stroke. The feasibility and acceptability objectives are described below.

1. Determine the feasibility and acceptability of the SNMES intervention post stroke, initiated in the first 2 weeks post admission and continued for 12 weeks.

Primary:

- Estimate screening, recruitment and attrition rates, and reasons for declining participation or leaving the study early (where possible).
- 3. Estimate adherence/engagement to the SNMES protocol, including number of sessions completed/total sessions in treatment protocol
- 4. Determine the acceptability of the outcome measures, data collection methods and data completeness

Inform the development of a definitive trial using the RAG (red, amber, green) methodology exploring recruitment rates, intervention adherence, and completeness of data collected/attrition).

The outcomes below are aligned to the study objectives to the left.

- 1. Interviews with people with stroke and their caregivers as well as focus groups with clinicians to explore their experience and acceptability of the SNMES intervention. Furthermore exploring/tracking adverse events and adverse reactions to treatment with SNMES (a common side effect of electrical stimulation is skin irritation from the electrode pads) will contribute to the feasibility and acceptability of the intervention.
- 2. Study enrolment rates (the number of patients who agree to take part of those eligible). Where possible reasons for not taking part will be recorded to help plan the definitive trial. Data will be collected on the time duration between hospital admission and randomisation.
- 3. Through a participant diary, records within the electrical stimulation machine, and participant/caregiver interviews estimate fidelity to the protocol and reasons why fidelity wasn't achieved. This will help the team to identify if the suggested dose is feasible and acceptable on a larger scale.
- 4. Through participant/caregiver interviews, therapist focus groups, and completeness of collected data explore the feasibility and acceptability of the outcome measures used. Acceptability of candidate outcomes measures and their variability to inform the selection of outcomes, including

IRAS ID: 332116

- 5. Collect data to inform sample size for a definitive trial
- 6. Determine whether the protocol can be incorporated within routine clinical practice
- 7. Assess the feasibility of delivering SNMES in a range of settings eg. hospital, rehabilitation, home.
- 8. Determine if the participant sample is representative of the local areas of recruitment and of national stroke survivors to develop and implement an inclusive recruitment strategy for the next stage.
- 9. Identify, measure, and value resources required to deliver the SNMES intervention
- 10. Pilot data collection tools to measure resource use in the follow-up period to inform the design of a future withintrial economic evaluation.

- the primary outcome, for a definitive trial, likely to be the 10 Metre Walk Test.
- 5. The data collected and outcome measures collected will inform the sample size estimation for the definitive trial.
- 6. Through participant/caregiver interviews and clinician focus groups explore the practicality of delivering the intervention in the proposed settings (such as the ability for people after stroke to carry out the SNMES intervention, if they need support, the level of caregiver or health care worker) support needed, and the ability to complete SNMES in a variety of settings. This will inform the methods of the definitive trial and if the stimulation protocol can be incorporated into routine practice.
- 7. Exploring how participants and caregiver experienced using SNMES in the different environments e.g. hospital, home, care home through the interviews
- 8. Exploring the diversity of the recruited sample and estimating if this is representative of the wider population of people with stroke will help to inform the development and implementation of an inclusive recruitment strategy for the next stage (definitive trial).
- 9. (addressing aim 9 and 10) Through the health economics and resource use questionnaire explore health resources used, costs of health resources, and costs of the interventions to inform the development of the health economics in the future trial.
- 10. Through the health economics and resource use questionnaire explore health resources used, costs of health resources, and costs of the interventions to

IRAS ID: 332116 Page **10** of **70**

		inform the development of the health economics in the future trial.
Secondary:	 Lower Limb Strength Muscle bulk Functional ability Walking ability Quality of life Resource use Disability Pain Sensation 	 Dynamometer, 30 Second Sit-Stand Test, NIHSS Stroke Scale (total score) Limb circumference Barthel Index, 10 Metre Walk Test, 30 Second Sit-Stand Test, Trunk Control Test 10 Metre Walk Test EQ-5D-5L Health Economics Resource Use Questionnaire Modified Rankin Scale Numerical Pain Rating Scale, and the Pain Visual Analogue Scale Sensation testing – Nottingham Sensory Assessment, Tactile Sensation Only
Intervention:	Treatment Intervention Group: SNMES to the stroke affected leg for 12 weeks + usual care Control Group: Usual care for 12 weeks Treatment intervention group stimulation process: SNMES delivers an electrical current via two independent channels. The motor points for stimulation are already known. The clinician will teach the participant and their family/caregivers how to apply, use, and remove the electrode pads and stimulation devices. The general procedure is described below. 1. Treatment with SNMES is provided using a 2 Channel battery operated device. 2. The motor points for the appropriate muscle is identified by the therapist. The clinician will mark this spot with a permanent marker for future sessions. 3. The electrode is placed on the muscle motor point. 4. The stimulator leads are connected to electrodes.	

IRAS ID: 332116 Page **11** of **70**

- 5. The limb is positioned in the splint/brace (if using) in a comfortable position to prevent the leg from moving during the stimulation.
- 6. The stimulator is set at a frequency of 50Hz, Pulse duration: 450 μs; ON:OFF time: 5:10 seconds and an intensity that produces a visible muscle contraction that is comfortable for the participant. The intensity is determined at each individual session.
- 7. The stimulation will continue for 45 contractions of each muscle group (12 minutes each muscle group – thigh and lower leg), which is around 30 minutes in total including set up and take off time. The muscles at the front and back of the thigh still be stimulated together, the muscles at the front and the back of the calf will be stimulated together.
- 8. When stimulation is complete the stimulator leads are removed from the electrodes.
- 9. The electrodes are removed from the skin and stored in their packaging for the next session.

This process is repeated for each muscle group.

Control group: Participants in the control group will not receive the electrical stimulation therapy intervention but will continue to receive all of their usual care.

iv. FUNDING AND SUPPORT IN KIND

Funder(s)	Financial and Non-Financial Support Given
National Institute for Health Research	Research grant, total value: £247,822
Research for Patient Benefit	

v. ROLE OF TRIAL SPONSOR AND FUNDER

University Hospitals Dorset NHS Foundation Trust will act as the sponsor for this trial and retain all roles and responsibilities this entails. This includes trial design, conduct, data analysis, interpretation, manuscript writing and dissemination of results.

The project is funded by the National Institute for Health Research (NIHR) Research for Patient Benefit (RfPB) funding stream.

vi. ROLES & RESPONISBILITIES OF TRIAL MANAGEMENT COMMITTEES / GROUPS

Trial Management Committees

Trial Management Group

STIM-STROKE Protocol v1.0 30-04-2025

IRAS ID: 332116 Page **12** of **70**

- The Trial Management Group (TMG) will have regular meetings to review the study progress, recruitment and data collection.
- The TMG will ensure all practical details of the trial are progressing well and working well and everyone within the trial understands them.
- TMG membership will incorporate the CI, co-investigators, public members, and a representative of the sponsor.

• Trial Steering Committee

- The TSC (Trial Steering Committee) will be a majority independent representation from outside the research project including members of the public.
- The TSC will meet regularly and send reports to the sponsor.
- The TSC members will be detailed in a separate Terms of Reference document.

Public Advisory Group

- The public advisory group (PAG) is comprised of people with stroke, caregivers to people with stroke.
- The PAG has contributed to the development of the participant information sheets and participant documents as well as study methods such as recruitment and outcome measures used.
- The PAG will have regular meetings to discuss the study progress and provide insight into any challenges the study is facing.
- The PAG will be involved throughout the project regarding study methods, data collection, and dissemination.

vii. PROTOCOL CONTRIBUTORS

Decisions will be made by the TMG but will require approval of the sponsor.

Name	Contribution to the Protocol	
[name]	Protocol development, research methodology, research background, dissemination, patient and public involvement strategy	
[name]	Protocol development, research methodology, background, dissemination, patient and public involvement strategy	
[name]	Protocol development, research methodology, dissemination	
[name]	Research methodology, development of health economics	
[name]	Research methodology, development of statistical approach	
[name]	Protocol development, research methodology, research background, dissemination	
[name]	Patient and public involvement strategy	

STIM-STROKE Protocol v1.0 30-04-2025

IRAS ID: 332116 Page **13** of **70**

viii. KEY WORDS

Stroke, electrical stimulation, motor recovery, lower limb,

ix. TRIAL FLOW CHART

Patient flow through the trial is described in Figure 1 below.

Figure 1 Trial Flow Chart

STIM-STROKE Protocol v1.0 30-04-2025

IRAS ID: 332116 Page **14** of **70**

Screening and Consent

Patients within two weeks of stroke will be screened by research practitioner and therapy team for eligibility (> 18 y/o, within 2-weeks of stroke, NIHSS score of ≥ 3 for the lower limb, unable to walk (with or without AD).

Patients that meet the eligibility criteria will be provided with a PIS and study introduction.

Informed consent or consultee consent will be obtained for those that want to take part.

Do not meet eligibility criteria or decline to participate (reason logged with permission)

NIHSS- National Institute of Health Stroke Scale

AD- assistive device

MRS - Modified Rankin Scale

NPRS – Numerical Pain Rating Scale

VAS – Visual Analogue Scale (pain)

[figure not shown]
30 SCSST – 30 Second Chair Sit-Stand Test

EQ-5D-5L - EuroQOL

SNMES- surface neuromuscular electrical stimulation

Baseline Assessment (Visit 1)

Demographic and stroke information, Trunk Control Test, MRS, NPRS, VAS< dynamometer (strength), limb circumference, 30 SCSST, EQ-5D-5L, Barthel Index, Nottingham Sensory Assessment.

Visit 2, 6 weeks Follow up

Dynamometer (strength), limb circumference, 30 SCSST, EQ-5D-5L, NPRS, VAS, Barthel Index, Nottingham Sensory Assessment, resource use questionnaire

Visit 3, 12 week Follow up

Dynamometer (strength), limb circumference, 30 SCSST, EQ-5D-5L, NPRS, VAS, Barthel Index, Nottingham Sensory Assessment, 10 Metre Walk Test, resource use questionnaire. SNMES group return stimulators.

Visit 4, 6 month Follow up - END OF STUDY

Dynamometer (strength), limb circumference, 30 SCSST, EQ-5D-5L, NPRS, VAS, Barthel Index, Nottingham Sensory Assessment, 10 Metre Walk Test, resource use questionnaire.

IRAS ID: 332116 Page **15** of **70**

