5.5. Baseline data

At baseline standardised outcome measures as well as demographic data will be collected. Demographic data collected from participants is based on research recommendations from Kwakkel and colleagues (2017) "Standardized Measurement of Sensorimotor Recovery in Stroke Trials: Consensus-Based Core Recommendations from the Stroke Recovery and Rehabilitation Roundtable. ²⁷ The demographic data collected is outlined below:

- Sex (assigned at birth)
- **Ethnicity**

STIM-STROKE Protocol v1.0 30-04-2025

IRAS ID: 332116 Page 38 of 70

- Medical history
- Premorbid function (Modified Rankin Scale)
- Education level
- Socioenonomic status via postcode
- Pre-stroke walking ability
- Pre-stroke living arrangements
- Stroke severity (NIHSS total score along with leg score)
- Active hand movement at stroke onset
- Stroke type (ischaemic/haemorrhagic), subtype (e.g. lacunar, large artery, othercarotid dissection) and location (e.g. internal capsule, middle cerebral artery)
- Thrombolysis or re-perfusion therapy
- Imaging -stroke confirmed on imaging (CT/MRI)

The data will be collected via chart review and through participant interview that the research practitioner will complete. This data will help the team to identify if the people recruited to the study are representative of the wider population of people with stroke.

The outcome measures are briefly described in the next section 5.6 and in Table 2. Appendix 3 details how the outcome measures will be completed.

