5.6. Trial assessments

Trial assessments will take place at baseline (Visit 1), 6-weeks after baseline (visit 2), 12-weeks after baseline (Visit 3), and 6-months after baseline (Visit 4). Please refer to Table 2 below for details regarding what data is collected at each visit.

Data at each visit will be collected by the research practitioner who is trained in carrying out each assessment and is documented in the delegation log.

The assessment window for Visit 2 is +/- 3 days to account for the weekend in which research practitioners would not be working. The assessment window for Visit 3 and visit 4 is +/- 7 working days. It is not expected that at Visit 3 or Visit 4 there will be rapid changes in function thus the longer assessment window.

Please see Appendix 3 for complete details and instructions for how to complete each assessment.

STIM-STROKE Protocol v1.0 30-04-2025

IRAS ID: 332116 Page **39** of **70**

Table 2 Schedule and Rationale of Assessments

Measure	Brief Description	Screening	Visit 1 (baseline)	Visit 2 (6- weeks) (+/- 3 days)	Visit 3 (12 - weeks) (+/- 7 days)	Visit 4 (6 months) (+/- 7 days)
NIH Stroke Scale (NIHSS)	Assess leg strength and ability of the stroke affected leg.	Х				
Trunk Control Test (unsupported sit)	Assesses trunk control, trunk strength, and unsupported sitting balance. There is evidence that better trunk control/sitting balance is associated with return to walking.		Х			
Walking ability	Assessment of if the person can walk without support. Participants will be included if they need support and help to walk.	Х				
Modified Rankin Scale	Assesses function and ability/disability after stroke.		Х			
Numerical Pain Rating Scale	Assessment of pain, rating scale from 0 no pain to 10 extreme pain in the stroke affected leg.		Х	X	Х	Х

Measure	Brief Description	Screening	Visit 1 (baseline)	Visit 2 (6- weeks)	Visit 3 (12 - weeks)	Visit 4 (6 months)
				(+/- 3 days)	(+/- 7 days)	(+/- 7 days)
Dynamometer	Assess the strength of muscles of the thigh and calf (Quadriceps, hamstrings, gastroc soleus, and anterior tibialis).		Х	Х	Х	Х
Oxford Grading Scale/Medical Research Council Scale	Measure of strength of the lower limb rating from 0/5 no muscle activity to 5/5 full strength against resistance.		Х	Х	Х	Х
30 second chair sit-stand test	Number of sit-to stands and stand-to sits in 30 seconds, this assesses functional ability, lower extremity muscle power, and muscles endurance.		Х	Х	X	Х

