Limb circumference	This is to assess muscle bulk and track potential muscle atrophy (muscle wasting) through measuring the circumference of thigh and calf with a tape measure.		Х	X	×	Х
EQ-5D-5L	Assessment of health-related quality of life.		Х	Х	Х	Х

Measure	Brief Description	Screening	Visit 1 (baseline)	Visit 2 (6- weeks) (+/- 3 days)	Visit 3 (12 - weeks) (+/- 7 days)	Visit 4 (6 months) (+/- 7 days)
Barthel Index	Assesses the ability to perform everyday activities e.g. dressing, bathing, walking, toileting.		Х	Х	X	Х
Nottingham Sensory Assessment – Tactile Sensation Subsection	Assesses the participants sensation to light touch on the lower limbs.		X	X	×	X
10 Metre Walk Test	Assesses walking ability and function. Measurement of the time it takes to walk 10 meters (with or without an assistive device).		(not completed due to inclusion criteria not being able to walk)	(not completed due to inclusion criteria not being able to walk)	X	X
Resource use Questionnaire	Health resources and therapy accessed (e.g. travel costs to appointments, number and length of healthcare visits, support at home) over the course of the study.			X	×	X

Measure	Brief Description	Screening	Visit 1 (baseline)	Visit 2 (6- weeks) (+/- 3 days)	Visit 3 (12 - weeks) (+/- 7 days)	Visit 4 (6 months) (+/- 7 days)
Semi- structured Interview participants with stroke and their caregivers.	Interviews with participants and their caregivers to explore their experience of the research, using SNMES, and their acceptability of SNMES. There will be n=12 participants interviewed from the intervention group, n=8 from the control group, and n=10 caregivers to the person with stroke in the intervention group.				X (convenience sample of participants with strokes will be interviewed) And (convivence sample of caregivers to participants with stroke receiving SNMES will be interviewed)	
Clinician Focus Group	Focus group with clinicians (n=10) will explore their perspectives on the feasibility and acceptability of the intervention and research processes.					X (convivence sample of clinicians supporting the intervention will take part in a focus group; at

STIM-STROKE Protocol v1.0 30-04-2025

IRAS ID: 332116 Page **43** of **70**

Measure	Brief Description	Screening	Visit 1 (baseline)	Visit 2 (6- weeks)	Visit 3 (12 - weeks)	Visit 4 (6 months)
				(+/- 3 days)	(+/- 7 days)	(+/- 7 days)
						the end of the intervention period)

Page **44** of **70**

IRAS ID: 332116

Modified Rankin Score

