11. DISSEMINATION POLICY

The findings of this study will be published in academic journals and presented at a national and an international conference. The first publication will be the research protocol. The CI and Project Manager and/or member of the research team will meet with the therapy teams and RNs at the collaborating trusts to share the research and for the teams get familiar with the study.

Annual reports will be sent to the collaborating trusts regarding the progress of the study. We will work with the PAG and public co-applicant to develop a public dissemination strategy including a plain English summary of the study findings and a video/audio version of the study findings.

The findings will be shared in collaboration with the PAG at the at the UK Stroke Forum, through the Stroke Association/local stroke groups, and social media (eg. Twitter). After completion of the study, the team will host an event with the public co-applicant for participants and their families to feed back the findings of the study.

If findings from this feasibility study warrant a full-scale trial we will submit an application to NIHR Health Technology Assessment programme. The findings will help to inform the develop and protocol of a definitive trial to explore if using SNMES on stroke-affected leg muscles in acute and subacute stroke contributes to earlier and improved walking and can slow or prevent muscle atrophy. If it is found that SNMES does contribute to earlier and improved walking and helps to maintain muscle bulk, it will be an intervention for individuals for whom there are currently few interventions early after stroke. Using SNMES in this way could be incorporated into the Stroke Guidelines which would lead to changes in practice and education. Earlier and improved walking would contribute to improved quality of life for people after stroke. Furthermore, if found to be effective this intervention could result in increased therapy time which aligns with the new National Clinical Stroke Guidelines

STIM-STROKE Protocol v1.0 30-04-2025

IRAS ID: 332116 Page **63** of **70**

recommending 3 hours of rehabilitation and 6 hours of activity per day for people following stroke during the recovery phase.

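### Three secondary outcomes in the trial summary have no follow-up assessment (the Modified Rankin Scale, the only disability measure, matters most), and the 10 Metre Walk Test is omitted at 6 weeks for a reason that describes entry only

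*Protocol*

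**What the plan says.** **Outcome list.** The secondary part of the trial summary (section iii) gives strength as "Dynamometer, 30 Second Sit-Stand Test, NIHSS Stroke Scale (total score"), functional ability as "Barthel Index, 10 Metre Walk Test, 30 Second Sit-Stand Test, Trunk Control Test", and then the disability and pain entries, which run together as "Modified Rankin Scale Numerical Pain Rating Scale, and the Pain Visual Analogue Scale". The Modified Rankin Scale is the only instrument set against disability.

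**Schedule.** Table 2 (section 5.6) marks NIHSS at screening only, described as "Assess leg strength and ability of the stroke affected leg". It marks the Trunk Control Test and the Modified Rankin Scale at Visit 1 only, and says of the Rankin: "Assesses function and ability/disability after stroke". Section 5.5 puts the same scale among the demographic items as "Premorbid function (Modified Rankin Scale").

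**Walk test.** Table 2 schedules the 10 Metre Walk Test at Visits 3 and 4. At both Visit 1 and Visit 2 it gives the same reason for leaving it out: "not completed due to inclusion criteria not being able to walk". Section 5.6 says this test will be the primary outcome if a definitive trial follows.

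**The concern.** An outcome measured only at or before baseline cannot describe what happens to participants afterwards, and no analysis plan can supply data that were never collected. Objective 4 and section 2.3 ask this study to judge the completeness, acceptability and variability of candidate outcome measures. For the three instruments above, that cannot be done at any follow-up.

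The walk-test reason carries an entry condition forward six weeks. Inclusion criterion 4 (section 4.1) requires that the person cannot walk or transfer independently within two weeks of stroke. It says nothing about week 6, by which time some participants may have regained walking. The test is the planned primary outcome of the next trial, and section 11 states that trial's question as whether the intervention "in acute and subacute stroke contributes to earlier and improved walking".

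**Working it through.** There is no stated figure to reproduce. The check matches each listed instrument to its scheduled visits and counts the follow-ups (Visits 2, 3 and 4).

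| Instrument | Role in trial summary | When scheduled (Table 2) | Follow-ups out of 3 |
|---|---|---|---|
| Modified Rankin Scale | Disability (sole measure) | Visit 1 | 0 |
| NIHSS total | Strength | Screening | 0 |
| Trunk Control Test | Functional ability | Visit 1 | 0 |
| 10 Metre Walk Test | Function, walking | Visits 3, 4 | 2 |
| Dynamometer, 30-second sit-stand, limb circumference, Barthel Index, EQ-5D-5L, pain rating, sensory assessment | Strength, bulk, function, quality of life, pain, sensation | Visits 1 to 4 | 3 each |
| Resource use questionnaire | Resource use | Visits 2 to 4 | 3 |

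**Is this a broken table?** No. The flow chart (section ix) independently shows the Trunk Control Test and Rankin at baseline, and none of the three instruments at 6 weeks, 12 weeks or 6 months.

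**How do other sections treat the three?**
- Section 5.5 uses NIHSS as a stroke-severity descriptor.
- Section 7.3.1 uses NIHSS and trunk control as baseline comparability variables.
- Sections 2.2 and 7.3.2 and Table 1 name none of the three as outcomes.
- The trial summary has nine secondary domains and Table 1 has eight. The one missing from Table 1 is disability.

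**What remains measured?** Strength keeps the dynamometer and sit-stand test, and function keeps the Barthel Index and sit-stand test, at all three follow-ups. Disability keeps nothing.

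**Which Rankin is it?** Section 5.5 describes a premorbid score, Table 2 a post-stroke one. The protocol does not say whether these are one item or two.

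**Does the Visit 2 walk-test reason hold?**
- The criterion cited fixes status at entry.
- Section 5.6 allows a longer window at Visits 3 and 4 because rapid change is not expected then, which suggests that function may still be changing at Visit 2.
- The 30-second sit-stand test is scheduled at Visits 1 and 2 in the same participants, so expected inability is not applied consistently as grounds for omission.

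**The case against.** The best defence is that the three instruments are a labelling slip in one table of the summary, since the rest of the protocol treats them as baseline variables or does not name them as outcomes. For NIHSS and Trunk Control this largely stands, and relabelling is enough. For disability it stands less well: the summary names it as a domain in its own right and gives it one instrument. Absence from sections 2.2 and 7.3.2 does not prove that it was dropped, because pain is absent from both and is still measured at every visit.

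On walking, the defence is that Table 1, Table 2 and the flow chart agree on Visits 3 and 4, so there is no contradiction, and that this study makes no between-group comparison. Both points are correct. The fault is in the stated reason, not in the consistency of the schedule.

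Three stronger readings are tempting, and the documents do not support them:
- **That no walking data exist before week 12.** The Barthel Index is collected at Visit 2, has an ambulation item, and is named in section 2.2 as a walking measure. Walking at 6 weeks is partly seen.
- **That every participant's week-6 visit is a lost walk test.** The protocol gives no rate of regained walking at 6 weeks, so the number of timed walks forgone cannot be stated.
- **That one Rankin score is made to serve two constructs.** Section 5.5 lists it with items from chart review and interview, and the flow chart shows demographic information and the Rankin separately. Two baseline items is an equally natural reading; the defect is that the protocol does not say.

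**Conclusion.** The point holds in two parts.

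First, the trial summary names three secondary outcomes that the schedule cannot deliver after baseline: 0 of 3 follow-ups each. The consequence is material for disability, which has no other measure, and minor for NIHSS and Trunk Control. The ambiguity over the baseline Rankin adds to the disability problem, because a premorbid score is not a trial outcome.

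Second, the reason given for omitting the 10 Metre Walk Test at Visit 2 does not apply at 6 weeks. What is lost is walking speed, and the proportion able to complete the planned definitive primary outcome, at that visit. Both remain available at 12 weeks and 6 months.

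Neither part affects the progression criteria in Table 3. Both limit what the study can say about candidate outcomes, and both should be corrected. The conclusion assumes that Appendix 3, which is cited for how assessments are carried out but is not in the text available, does not alter the visit schedule; nothing in the protocol suggests that it does.

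**What to change.** 1. Reconcile the trial summary with Table 2 and the flow chart on disability: either add a current Modified Rankin at Visit 4 (optionally also at Visit 3), or remove disability from the secondary outcomes.
2. List premorbid and current Rankin as two separately labelled baseline items in section 5.5, Table 2 and the CRF.
3. Move NIHSS total and the Trunk Control Test from the outcome list to baseline descriptors, in line with section 7.3.1.
4. Schedule the 10 Metre Walk Test at Visit 2 for participants able to walk, record the others as unable, and delete the inclusion-criterion note at that visit. Update Table 1 and the flow chart to match.

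The cost is protocol and CRF edits, plus what should be a few minutes at visits that already take place; the protocol gives no administration times, so the minutes are a judgement. Relabelling alone (item 3, and the removal option in item 1) adds no assessment time.
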